#### **Subject Study ID Assignment Log Sample:**

Assignment log will go from study ID 1 to study ID 24. Each one will correspond to a randomized number. Table 1 below is an example of the excel sheet that will be used.

Table 1 – Subject Study ID Assignment Log Sample						
Randomization #	Subject Name	MR#	Study ID	Treatment Assignment	Date Randomized	Initials
CH1			1	PRP		
CH2			2	PRP	i.	
CH3			3	PRP	ii.	
CH22			22	Conservative	iii.	
CH 23			23	Conservative		
CH 24			24	Conservative		

Once randomization is performed, a randomized assignment list will also be filled out. Each randomization number will correspond to either of two treatments (PRP-Conservative).

#### **Randomized Assignment Sample List**

Table 2 – Randomized Assignment List Sample	
Enrollment	Randomization

Study ID #	Subject Name	Subject MR#	Date Enrolled	Initials	Randomization #	Date Randomized	Initials
01-A					CH1		
02-B					CH2		
03-C					CH3		
04-D					CH4		
05-E					CH5		
06-F					CH6		

### Subject ID Assignment Log

[figure not shown]
Randomization #: CH-F-1 Treatment Assignment: PRP

Study ID #: \_\_\_\_\_

Date envelope opened: \_\_\_\_ / \_\_\_\_ / \_\_\_\_

Time opened: \_\_\_\_ : \_\_\_\_ (24 hour clock)

Signature of the person who is randomizing the subject: \_\_\_\_\_

## **Treatment Regimens and Dosing**

All eligible patients will be randomized to a treatment or conservative therapy group. Those within the conservative therapy group will be fitted with a hinged brace locked in extension, with weight bearing as tolerated and crutches for those with painful to weight bear, complete rest from impact activities, progressing to weight bearing as tolerated for 6 weeks, and then followed according to the Orthopedic department's protocol for OCD.

The PRP treatment group will receive three injections per randomization table into the symptomatic knee, they will also be fitted with a hinged brace locked in extension, with weight bearing as tolerated and crutches for those with pain upon weight bear, complete rest from impact activities with progression to weight bearing as tolerated for 6 weeks, and then followed according to the Sports Medicine department's protocol for OCD. Study subjects in the PRP treatment arm will receive a total of 3 intra-articular injections, one week apart +/- 10 days. All subjects will have a physical exam performed to assess their knee function.

If a patient has bilateral symptomatic knee osteochondritis dissecans, the more symptomatic side will be injected while the less symptomatic side will not be injected, the patient will then follow the same treatment regimen as the treatment group on the treated side.

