**2. Specific Aims:**

In adolescents with osteochondritis dissecans of the knee:

**Aim 1.** Compared to conservative therapy alone, determine whether intra-articular platelet injections combined with conservative therapy lead to greater cartilage healing.

**Efficacy Endpoint** – Measurement by glycosaminoglycan (GAG) content (T1GD) on dGEMRIC, or by healing changes of MRI diagnostic cartilage sequences, using the DiPaola classification system.

**Aim 2.** Compared to conservative therapy, determine whether intra-articular platelet injections lead to improvements over time in:

**Efficacy Endpoint 2.1.** Pain, as measured by the pain subscale of the KOOS-child.

**Efficacy Endpoint 2.2.** Performance of activities of daily living, as measured by the ADL subscale of KOOS-child.

**Efficacy Endpoint 2.3.** Sport performance, as measured by the sports subscale of the KOOS-child.

**Efficacy Endpoint 2.4.** Overall function and symptom reduction, as measured by the pedi-IKDC.

**Aim 3.** Correlate dGEMRIC findings or MRI diagnostic cartilage sequence findings on imaging studies with measures of functional recovery and symptom reduction.

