#### **4. Research Methods**

We propose a randomized controlled clinical trial in children (aged 10-17) with osteochondritis dissecans (OCD) comparing the use of platelet-rich plasma (PRP) therapy and conventional therapy compared to conventional therapy alone.

The goal of this research is to test the hypothesis that intra articular injections with autologous PRP will improve symptoms, recovery time, and imaging appearance using delayed gadolinium enhanced MRI of cartilage (dGEMRIC) or MRI diagnostic cartilage sequence findings in patients suffering from stable juvenile OCD of the knee when compared to conservative therapy. Specifically, we aim to determine whether intra-articular platelet injections when compared to conservative therapy over time, lead to greater cartilage healing (measured by gadolinium accumulation or measured by healing on Non-contrast MRI, utilizing the DiPaola classification system), improvement in pain, improvement in performance of activities of daily living, improvement in sport performance, and improvement in overall function and symptom reduction.

Finally, we aim to determine if dGEMRIC findings or MRI diagnostic cartilage sequence findings on imaging studies correlate with measures of functional recovery and symptom reduction.

All protocol procedures other than patient randomization, PRP injections, and the 6 month dGEMRIC or Non-Contrast MRI are considered routine standard of care procedures. These three procedures are being conducted for research purposes in this study.

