#### **Pre-Screening Visit**

Study subjects will be recruited from current patient population at Children's Hospital Colorado or first time patients of [name]/ [name] or their colleagues at the Children's Hospital Sports Medicine Clinic. They will be identified and recruited during routine office visits. Study subjects may also come directly to the PI/Research Associate through the clinicaltrials.gov website. The initial MRI scan, initial x-rays, and any follow-up x-rays will be performed as standard of care and will follow hospital policy, and they will be used to assess and confirm eligibility. Female patients included in the study, over the age of 12 who have begun menstruation will undergo a urine pregnancy test prior to the research MRI obtained at 6 months.

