[http://www.sportsmed.org/uploadedFiles/Content/Medical\\_Professionals/Research/Grants/IKDC\\_Forms/Pedi-IKDC%20Form.pdf](http://www.sportsmed.org/uploadedFiles/Content/Medical_Professionals/Research/Grants/IKDC_Forms/Pedi-IKDC%20Form.pdf)

Clinical follow up will also be performed following injections or the commencement of conservative therapy at 6 weeks, 12 weeks, 6 months, 9 months, and 12 months by [name]/[name] or their colleagues on the CHCO main campus or one of the following satellite locations (South, Parker, Centennial, Uptown/St Joseph's or Broomfield). The clinical findings documented will include presence or absence of a joint effusion, overall range of motion, presence or absence of joint line tenderness and positive or negative Wilson's test 6 week follow up for both groups will also include radiographic evaluation, which is standard of care. If

the patient is clinically or radiographically improving, physical therapy will be started as standard of care, following the same treatment protocol initially with closed kinetic chain, non-impact exercises. Patients will then slowly return to impact activities as tolerated over 3 to 4 months.

A patient Timeline of Activity has been created for each arm of the study (see two attachments). The Timeline describes the weekly and monthly events that will occur during this study and can be handed to the patient following the consent and randomization process.

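### The treatment section sends the two arms to different departments' OCD protocols after week 6; if that is followed and the protocols differ, later care cannot be separated from PRP

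*Combined protocol and SAP*

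**What the plan says.** Section 4, Research Methods, describes a trial "comparing the use of platelet-rich plasma (PRP) therapy and conventional therapy compared to conventional therapy alone". Aim 1 in section 2 frames the question in the same way: "Compared to conservative therapy alone, determine whether intra-articular platelet injections combined with conservative therapy lead to greater cartilage healing".

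Treatment Regimens and Dosing describes essentially the same hinged brace, weight bearing as tolerated and rest from impact in both arms. It then separates them. The conservative arm has this regimen "for 6 weeks, and then followed according to the Orthopedic department's protocol for OCD". The PRP arm has it "for 6 weeks, and then followed according to the Sports Medicine department's protocol for OCD". Neither departmental protocol is described, and the two are not said to be the same.

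The section on surveys and clinical assessments describes the 6-week visit for both groups. It then says that patients who are improving start physical therapy "following the same treatment protocol initially with closed kinetic chain, non-impact exercises", and adds: "Patients will then slowly return to impact activities as tolerated over 3 to 4 months". It also mentions a Timeline of Activity for each arm. Those two attachments are not in the file.

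**The concern.** An add-on design isolates the added treatment only if the background care is the same in both arms. Here the section that defines treatment attaches a different department's protocol to each arm, from week 6 onwards. The follow-up section points the other way. If the two protocols differ, staff cannot follow both sections.

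Literal use is plausible. Patients and parents know the assignment, the randomization envelope holds handouts and instructions for the assigned arm, and each arm has its own timeline. Arm-specific instructions therefore have a route to the patient.

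At stake is what a difference between arms would mean. The 6-month MRI and most of the patient-reported follow-up come after week 6. Under literal use with differing protocols, a difference could reflect PRP, rehabilitation or both.

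**Working it through.** The plan gives no figure on this point to reproduce. The check compares the sections and then works out what literal use would imply.

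**Sections side by side**

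| Section | Implication for care after week 6 |
|---|---|
| Treatment Regimens and Dosing | Orthopedic protocol (conservative), Sports Medicine protocol (PRP) |
| Specific Aims; Research Methods | Same background care, PRP added in one arm |
| Clinical assessments | One physical therapy pathway, described after a visit for both groups |
| Research Methods, list of research procedures | Only randomization, PRP injections and the 6-month MRI are outside routine care |
| Randomization | Arms described as standard of care with or without PRP |
| Treatment schedules, both arms | Follow-up assessments under the hospital's standard of care |
| Table 3 | Later physical exams are standard of care in both arms |
| Pre-Screening Visit | Clinic recruitment through physicians "or their colleagues at the Children's Hospital Sports Medicine Clinic" |

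The first row stands alone against the rest, but it is the row that defines treatment.

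**Separability under literal use with differing protocols.** Let A = 1 for PRP and R = 1 for the Sports Medicine protocol. With 12 patients per arm, R = A for all 24. A design matrix with intercept, A and R has rank 2 for 3 columns. The difference in means splits as

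E(PRP, Sports) − E(no PRP, Ortho) = [E(PRP, Sports) − E(no PRP, Sports)] + [E(no PRP, Sports) − E(no PRP, Ortho)].

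The first bracket is the effect of PRP and the second is the effect of the protocol. No patient is observed under (no PRP, Sports), so only the sum can be estimated. The Aim 1 and Aim 2 models have no rehabilitation term, and adding one would not help. This spells out the consequence of the condition; it is not evidence that the condition holds.

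**Period affected before the MRI**
- One month = 365.25 / 12 / 7 = 4.35 weeks, so six months = 26.1 weeks.
- From week 6 to the MRI: 26.1 − 6 = 20.1 weeks.
- Share: 20.1 / 26.1 = 0.77.

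This takes week 6 and month 6 from one origin, as the single time axis of Table 3 suggests. The text is less clear. The MRI is dated from the initial visit, while the follow-up section says: "Clinical follow up will also be performed following injections or the commencement of conservative therapy at 6 weeks, 12 weeks, 6 months". If the treatment clock starts g weeks after the initial visit, the share is (20.1 − g) / 26.1. As an assumed range, g = 0 gives 77%, g = 1 gives 19.1 / 26.1 = 73%, and g = 2 gives 18.1 / 26.1 = 69%.

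**Surveys affected.** The Aim 2 model uses 6 weeks, 12 weeks, 6 months, 9 months and 12 months. Four of these five come after week 6.

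**The case against.** The strongest reply is that this is a drafting slip with no consequence. Most of the rows above point to one common standard of care, and harm needs two things that the documents do not show: literal use of the treatment section, and protocols that differ in content. That stands. It limits the severity and keeps the confounding conditional. It does not justify leaving the text alone, because the section that defines treatment still contradicts the trial's own contrast. Nor does the follow-up section settle the matter: its reference to the same protocol has no explicit referent, although sameness across arms is the natural reading.

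A reader might go further in three ways, none of which the documents support.

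- **That the trial is confounded.** Neither protocol's content is given, so a difference in care is possible but not shown.
- **That the 3 to 4 months of return to impact measures the exposure.** That timing belongs to the common pathway in the follow-up section. Neither department is known to use it, and its starting point after the first non-impact exercises is not stated. It cannot size a split that exists only if the treatment section is taken literally.
- **That the protocol followed is not recorded anywhere.** The weekly Compliance Survey stops at week 6, but it does not follow that no other form captures later care. The available text describes no such field. The case-report forms and attachments are not in the file, and clinical encounter notes exist for the follow-up visits.

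**Conclusion.** The inconsistency is real and is in the current text: two departments' protocols are assigned by arm after week 6, against an intended contrast of PRP added to the same background care. The confounding is conditional on the treatment section being followed as written and on the two protocols differing. Under both conditions, background care would coincide completely with assignment over the MRI and survey periods worked out above, and no analysis of these data could separate the two. If either condition fails, there is no bias and only the wording needs correcting. The documents give no figure for the effect of a rehabilitation difference on T1GD, Di Paola grade or survey scores, so no size of bias is claimed. Severity is low to moderate.

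**What to change.** In Treatment Regimens and Dosing, name one post-week-6 OCD protocol for both arms. Which one is the sponsor's choice; the follow-up section names no department. Use the same criteria in both arms for starting therapy and for returning to impact, and make the two Timeline of Activity attachments agree with them.

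For patients already past week 6, establish from the medical record which protocol was followed and tabulate it by arm beside the Aim 1 and Aim 2 results. If the arms did follow different protocols, describe the contrast as PRP plus one rehabilitation protocol versus the other protocol without PRP.

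Do not adjust for the dates of starting therapy or returning to impact. Recovery time is part of the hypothesis and return to impact depends on tolerance, so these dates may themselves reflect an effect of PRP.

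The cost is one phrase, a check of two existing attachments and a record check in at most 24 patients. No visit or procedure is added.

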### **PRP Dosing and Protocol**

Several phlebotomy and processing kits are FDA approved for safe and rapid preparation of PRP, and are commercially available. Dose, preparation and regimen of intra-articular injections of PRP have been variable in the literature. Doses vary between one to three injections, given consecutively within one or two week intervals [30].

For this protocol, we will use the FDA approved Harvest PRP Procedure Pack kit (BK000037) from Terumo-Harvest. The Harvest PRP system is designed to be used for the safe and rapid preparation of autologous platelet-rich plasma (PRP) from a small sample of blood at the patient's point of care. Each Harvest PRP kit consists of components necessary to collect whole blood from the patient into a syringe containing anticoagulant and to separate the centrifuged sample into fractions (including the one containing platelet-rich plasma).

Each PRP preparation requires a total of 30 mL of peripheral blood. Blood will be obtained via direct venipuncture by radiology nursing staff, [name] or one of the study team physicians using the provided tourniquet and butterfly needle. Blood will be collected into a 30mL syringe containing 3mL ACDA. 30 mL of acid-citrate-dextrose Formula (ACD-A) anticoagulated whole blood will be processed according to the manufacturer's directions. In brief, the anticoagulated whole blood will be transferred into the first chamber, which has a floating shelf of a proprietary density. Following an initial centrifugation of 4 minutes, the supernatant, containing plasma and the cellular elements less dense than the floating shelf, will be decanted into the second chamber of the disposable and centrifuged for 10 minutes. The

PRP volume of 3 or 4 mL will be prepared using the appropriate spacer to remove the desired volume of the supernatant platelet-poor plasma (PPP). The PRP is resuspended in the remaining volume of PPP.

This PRP preparation process takes place in the Interventional Radiology suite, Flourosopy suite or a Co-Investigator's clinic office.

All sites/clinics are amenable for sterile procedures.

Immediately prior to PRP injection into the study subject, calcium chloride is drawn up from the activator ampoule and will be added to the PRP. The activated PRP will then be injected in its entirety into the knee joint. All the preparation is performed under strict aseptic technique and follows the appropriate manufacturer instructions.

Harvest PRP kits and centrifuge are provided free of charge from the vendor, Harvest TERUMOBCT . The PRP kit/device is not intended to provide data to support the claim for the device but rather to study the clinical effect of the device.

### **PRP and Conservative Treatment Schedules Following Randomization**

Patients will be assessed during a standard of care visit for basic eligibility to participate in this study or via a telephone call with one of the Study Team Physicians. Patients who meet the basic inclusion criteria will be given the option of participating in the study either at this first visit, or a subsequent visit after they are given the opportunity to review the informed consent documents.

**PRP study participants:** A total of 8 visits (9 visits, if consent is done as a separate visit) are expected during a 12-month time period for patient follow up. All initial visits will include a patient assessment using basic standard of care to determine eligibility for study enrollment. This first visit, if the patient decides to enroll, may also include patient consenting. The second through fourth visits, one week apart +/- 10 days, will include treatment with PRP injections. After the 3rd injection, subjects will be seen for clinical evaluation and survey assessment per schedule of assessment below as the standard of care. MRI obtained prior to enrollment for initial evaluation of the knee is performed as standard of care in the management of knee OCD. The research MRI performed at 6 months post treatment will be obtained to assess cartilage healing utilizing physiologic imaging of cartilage with the dGEMRIC technique or a Non-contrast MRI of the knee.

The three injection visits (1 through 3) will take approximately 30-45 minutes per visit. This includes time for the baseline patient reported outcomes and blood draw.

Follow up visits (5 through 9) last around 30 minutes and will include patient reported surveys, physical examination, and x-rays to assess the injury in accordance with the standard of care at CHCO.

**Conservative treatment participants:** A total of 5 visits (6 visits, if consent is done as a separate visit) are expected during a 12-month time period for patient follow-up. The first visit will include initial assessment and possible recruitment. The second through fifth visits will include patient reported surveys, physical examination and x-rays to assess the injury in accordance with the standard of care at CHCO. MRI obtained prior to enrollment for initial evaluation of the knee is performed as standard of care in the management of knee OCD. The research MRI performed at 6 months post treatment will be obtained to assess cartilage healing utilizing physiologic imaging of cartilage with the dGEMRIC technique or a Non-contrast MRI of the knee. **Please refer to the patient schedule matrix, Table 3, below.**

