Battaglia et al recently reported the outcomes of injection of PRP for OA of the hip. Twenty patients, with a mean age of 52 years, who presented symptomatic OA of the hip were treated with a total of 3 intrarticular injections of PRP. Patients were prospectively evaluated at 1, 3, 6, and 12 months follow up. All patients had significantly improved clinical symptoms. No major complications or adverse events occurred at the moment of injection or in the follow-up period. Ten patients reported a slight pain during or after the injection, which spontaneously resolved in 1 or 2 days [30].

Gillis et al evaluated autologous chondrocyte transplantation in patients with full thickness chondral lesions of the knee utilizing dGEMRIC to indirectly quantify the GAG content of cartilage at the site of transplant, adjacent to the site of transplant, and distant to the site of transplant. The study demonstrated that GAG levels in grafts that had been implanted at 12 months or greater had GAG levels comparable to adjacent and remote cartilage. [31]

Typically, patients with Juvenile Osteochondritis Dessicans will heal without treatment within a 12 month period, therefore it was recently decided that the research dGEMRIC MRI would be performed 6 months from the time of the consent instead of 12 months. [32]

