### **Research MRI utilizing dGEMRIC or Non-contrast MRI**

Once the intrarticular PRP injections have been administered, a follow-up MRI will be performed utilizing dGEMRIC or Non-contrast MRI at 6 months from the initial visit. Mean T1 values on dGEMRIC will be calculated by drawing a region of interest at the site of hyaline cartilage pathology, adjacent to the site of pathology within the hyaline cartilage, and distant to the site of pathology within the hyaline cartilage on initial and follow up imaging. If the follow-up imaging is with a Non-contrast MRI, the DiPaolo classification system will be used to quantify interval change.

Knee MRI with dGEMRIC will be performed in the standard manner. Upon arriving to the radiology department for the MRI, a pregnancy test will be administered for all female participants of child bearing potential. An institutional MRI screening form will be given to each patient and parent and reviewed with the MRI technologist. If there is any retained metal (pacemaker, metallic bb, orthopedic hardware), MRI will not be performed. If there is no contradiction to MRI based on the institutional screening form, the patient will have an IV placed. Using weight based dosing, .04 ml/kg, injection of gadolinium will be administered. The patient will then be asked to exercise for 30 minutes, which will be performed by walking around the hospital. The patient will then return to the MRI suite in the department of radiology. Standard screening for retained metal will be performed prior to entering the MRI scanning area. If the parent/guardian wishes to accompany the child for the MRI scan, they will be screened in identical fashion. In the MRI scanner, the patient will be required to lie still for approximately 1 hour, the duration of the scan. The patient will have the option of watching a

movie or listening to music on ipod or similar device (plugged in outside the scanner in technologist area) during imaging. No sedation will be given. There is no ionizing radiation associated with MRI.

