C = PRP Arm – Physical Exam will be performed for research only and will be take place prior to the injection of PRP.

D = X-rays are performed as standard of care depending on the conditions of each individual patient.

R=Research \* 6 months from initial visit

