## **Safety Measurements**

The nature, onset, duration, severity, and outcome of all adverse events, as well as any association of an adverse event related to the study medication, will be assessed and documented at each visit. Patients will be asked to avoid intake of NSAIDs. If symptoms require pain medications during the initial follow up period (6 months after last injection), NSAID consumption will be recorded, as well as other pain medications taken. Patients will be allowed to have non-NSAIDs rescue medication as needed to treat pain. This includes acetaminophen and in select cases opioids such as Vicodin or Percocet. To evaluate the safety profile of the treatments, all complications and/or adverse events will be reported with their level of severity and their causal relationship to the study treatment.

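### The 6-month MRI and the follow-up visits are counted from conflicting starting points, some of which can make elapsed time differ between the arms

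*Combined protocol and SAP*

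**What the plan says.** The 6-month research MRI supplies the primary endpoint (Power Analysis names Aim 1). Current text gives it three starting points:

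- PRP and Conservative Treatment Schedules Following Randomization, in identical words for each arm: "The research MRI performed at 6 months post treatment will be obtained to assess cartilage healing".
- Research MRI utilizing dGEMRIC or Non-contrast MRI: "a follow-up MRI will be performed utilizing dGEMRIC or Non-contrast MRI at 6 months from the initial visit". The Table 3 footnote agrees: "6 months from initial visit".
- Preliminary Studies (section 3e): "the research dGEMRIC MRI would be performed 6 months from the time of the consent instead of 12 months".

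Clinical follow-up has an anchor that differs by arm. The section on surveys and clinical assessments places it "following injections or the commencement of conservative therapy at 6 weeks, 12 weeks, 6 months, 9 months, and 12 months". The schedule section likewise puts PRP follow-up after the third injection, but refers to Table 3 for the dates. Table 3 is one calendar for both arms. Safety Measurements defines the period for recording pain medication as "during the initial follow up period (6 months after last injection", an event that controls never have.

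For the conservative arm the schedule section says "The second through fifth visits will include patient reported surveys, physical examination and x-rays". That is four follow-up visits.

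**The concern.** Section 3e says that juvenile lesions usually heal untreated inside 12 months. Time since the start of care is therefore itself expected to improve the outcome. The Aim 1 and Aim 2 models represent time by nominal visit and adjust only for age, so a visit labelled 6 weeks or 6 months is treated as the same point in healing in both arms. If one arm's clock starts later, its patients are seen further into natural recovery under the same label, and the model attributes the difference to treatment. With 12 patients per arm and a single follow-up scan, the analysis has little means of separating the two afterwards.

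**Working it through.** The plan gives no figure on timing to reproduce, and its stated power of 0.93 does not enter this check.

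**Inputs from the plan.** Three injections, one week apart +/- 10 days (Treatment Regimens and Dosing); Table 3's injection row shows +/- 7 days. Bracing for 6 weeks in both arms. Table 3 windows of +/- 1 week at Week 6, Week 12, Month 6 and Month 9, and +/- 2 weeks at Month 12. SD 50 ms, planned difference 85 ms, 12 per arm (Power Analysis).

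**Assumptions.** Therapy in controls and the first injection in the PRP arm both start on day 0; 6 months is 182 days.

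**Step 1: shift under each reading.** The nominal last injection is on day 2 x 7 = 14, and bracing ends on day 42.

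| PRP clock starts | Control clock starts | PRP minus control |
|---|---|---|
| Initial visit or consent | Same | 0 days |
| Last injection (day 14) | Start of therapy (day 0) | +14 days |
| Last injection (day 14) | End of bracing (day 42) | -28 days |
| End of bracing (day 42) | End of bracing (day 42) | 0 days |

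**Step 2: relative size of +14 days.** 14/42 = 33% at 6 weeks; 14/84 = 17% at 12 weeks; 14/182 = 8% at 6 months. Fourteen days exceeds the 7-day window at every visit up to Month 9 and just fits the Month 12 window. Injections in Weeks 1 to 3 put six weeks after the third at about Week 9, while Table 3 allows Weeks 5 to 7. Staff cannot follow both rules.

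**Step 3: individual extreme.** 2 x (7 + 10) = 34 days, or 2 x (7 + 7) = 28 days on Table 3's injection row. These are limits for one patient, not expected means; the same tolerance also shortens intervals.

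**Step 4: size on T1GD.** The documents give no healing rate. Assume a linear natural gain of G ms per year; the artefact is G x 14/365.

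| Assumed G (ms/year) | Artefact (ms) | Share of 85 ms |
|---|---|---|
| 25 | 1.0 | 1.1% |
| 50 | 1.9 | 2.3% |
| 85 | 3.3 | 3.8% |
| 170 | 6.5 | 7.7% |

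On the reversed reading (28 days) the figures double and favour controls: 1.9 to 13.0 ms.

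**Step 5: effect on false positives.** For a two-group comparison of 6-month values, SE = 50 x sqrt(2/12) = 20.4 ms and the noncentrality is artefact/SE, from 0.05 to 0.32, on 22 df. Over this range of G at 14 days, the two-sided error at nominal 0.05 becomes 0.050 to 0.061, and at 0.05/3 it becomes 0.0168 to 0.0216. This is a simplified comparison, not the four-way interaction that Aim 1 tests first.

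**Step 6: Aim 2 scores.** No rate is given here either. A linear gain of 10, 20 or 30 points per year gives 0.4, 0.8 or 1.2 points for 14 days (gain x 14/365). Faster early recovery would enlarge this at the 6- and 12-week visits.

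**Step 7: visit count.** Controls' second through fifth visits make four follow-ups. The survey schedule, the clinical follow-up paragraph and the Aim 2 model each need five (6 weeks, 12 weeks, 6, 9 and 12 months), and the PRP arm has five (visits 5 through 9).

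**The case against.** A reader might infer that the PRP arm is systematically assessed later and that every between-arm comparison is tilted in its favour. The documents do not support that, for these reasons:

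- Table 3 is a common calendar to which the schedule section refers for both arms. It appears to place randomisation, baseline surveys and the first injection together in Week 1. If it governs, there is no shift.
- The imaging section and the Table 3 footnote align the MRI across arms. Initial visit and consent both precede randomisation, so they cause inconsistency but no arm difference.
- The post-treatment wording is the same for both arms. Depending on what ends treatment in controls, the shift can be positive, zero or negative.
- The only explicitly arm-specific anchor covers clinical findings such as effusion and range of motion, which are not modelled outcomes. The KOOS and IKDC schedule is stated for all patients without reference to the injections.
- A 34-day mean shift would need every PRP patient at the limit of tolerance.

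All of this stands, and it removes any claim of a known direction or a large effect. It does not remove the contradiction. No passage says which anchor prevails, and the 14-day gap does not fit the windows through Month 9. The schedule section also describes PRP survey assessment as following the third injection, so the surveys are not clearly protected. The visit count is a separate slip with no bearing on time zero.

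**Conclusion.** The point holds as an unresolved contradiction that can make elapsed time differ by arm, with nothing in the models to adjust for it. Only the post-treatment and after-injections anchors can do so. The nominal shift is 14 days later for PRP on one reading, and it reverses for the MRI if controls are counted from the end of bracing, so the direction is uncertain. For T1GD the likely effect is small: about 1 to 6.5 ms at 14 days against 85 ms planned, resting wholly on an assumed linear gain of 25 to 170 ms per year. The early Aim 2 visits are the most exposed, because 14 days is a third of the 6-week interval. It should be corrected because it touches the primary comparison and the remedy is nearly free.

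**What to change.** Define one arm-neutral time zero, the date of randomisation, for the research MRI, the KOOS-child and Pedi-IKDC surveys, the follow-up assessments and the medication-recording period. This fits Table 3's common calendar. Reconcile to it section 3e, both arms' paragraphs in the schedule section, the clinical follow-up paragraph, the imaging section, the Table 3 footnote and Safety Measurements.

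Record the actual date of every scan and survey. As a sensitivity analysis, replace nominal visit in the mean model by days since randomisation, keeping nominal visit to index the covariance. This is a check and not a substitute for the common anchor: if all PRP visits were late by a similar amount, elapsed days and arm would be hard to separate in 24 patients.

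Separately, reconcile the conservative arm's four follow-up visits with the five required elsewhere.

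The cost is a wording amendment. Where PRP assessments are now timed from the last injection, they move by about two weeks. Sample size, stated power and treatment do not change.
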